3.1 ECG

These tables will be produced for QTcF,QT, PR, RR, QRS.

OTcF

Table 3.1.1 Summary of QTcF by Treatment Arm

QTcF (Friderica's correction)	Arm 1 D0 (N=x) n (%)	Arm 2 D400 (N=x) n (%)	Arm 3 D800-OD (N=x) n (%)	Arm 4 D1200 (N=x) n (%)	Arm 5 D800-BD (N=x) n (%)	Total (N=x) n (%)
QTcF < 450 ms	xx (xx.x %)	xx (xx.x %)	xx (xx.x %)	xx (xx.x %)	xx (xx.x %)	xx (xx.x %)
450 ms ≤ QTcF <480 ms	xx (xx.x %)	xx (xx.x %)	xx (xx.x %)	xx (xx.x %)	xx (xx.x %)	xx (xx.x %)
480 ms ≤ QTcF < 500 ms	xx (xx.x %)	xx (xx.x %)	xx (xx.x %)	xx (xx.x %)	xx (xx.x %)	xx (xx.x %)
QTcF ≥ 500 ms	xx (xx.x %)	xx (xx.x %)	xx (xx.x %)	xx (xx.x %)	xx (xx.x %)	xx (xx.x %)

Table 3.1.2 Participants Proportion of QTcF Changes from Baseline by Treatment Arm

QTcF Changes	Arm 1	Arm 2	Arm 3	Arm 4	Arm 5	Total
from Baseline	D0	D400	D800-OD	D1200	D800-BD	(N=x)
	(N=x)	(N=x)	(N=x)	(N=x)	(N=x)	n (%)
	n (%)					
Decrease (an increase < 0 ms)	xx (xx.x %)	(xx.x %)				
0 ≤ Increase < 30 ms	xx (xx.x %)	xx (xx.x %)				
30 ms ≤ Increase < 60 ms	xx (xx.x %)	(xx.x %)				
Increase ≥ 60 ms	xx (xx.x %)	xx (xx.x %)				

Table 3.1.3 Summary of QTcF Actual Value by Visit

Visit	Arm 1 D0 Mean (SE) /N*	Arm 2 D400 Mean (SE) /N	Arm 3 D800-OD Mean (SE) /N	Arm 4 D1200 Mean (SE) /N	Arm 5 D800-BD Mean (SE) /N
Baseline	xx (xx.x)/N	xx (xx.x)/N	xx (xx.x) / N	xx (xx.x) / N	xx (xx.x) / N
Week 01	xx (xx.x) / N	xx (xx.x) / N	xx (xx.x) / N	xx (xx.x) / N	xx (xx.x) / N
Week 02	xx (xx.x) / N	xx (xx.x) / N	xx (xx.x) / N	xx (xx.x) / N	xx (xx.x) / N
Week 03	xx (xx.x) / N	xx (xx.x) / N	xx (xx.x)/N	xx (xx.x) / N	xx (xx.x) / N
Week 04	xx (xx.x) / N	xx (xx.x) / N	xx (xx.x) / N	xx (xx.x) / N	xx (xx.x) / N
Week 05	xx (xx.x) / N	xx (xx.x) / N	xx (xx.x) / N	xx (xx.x) / N	xx (xx.x) / N
Week 06	xx (xx.x) / N	xx (xx.x) / N	xx (xx.x) / N	xx (xx.x) / N	xx (xx.x) / N
Week 07	xx (xx.x) / N	xx (xx.x) / N	xx (xx.x) / N	xx (xx.x) / N	xx (xx.x) / N
Week 08	xx (xx.x) / N	xx (xx.x) / N	xx (xx.x) / N	xx (xx.x) / N	xx (xx.x) / N
Week 09	xx (xx.x) / N	xx (xx.x) / N	xx (xx.x) / N	xx (xx.x) / N	xx (xx.x) / N
Week 10	xx (xx.x) / N	xx (xx.x) / N	xx (xx.x) / N	xx (xx.x) / N	xx (xx.x) / N
Week 11	xx (xx.x) / N	xx (xx.x) / N	xx (xx.x) / N	xx (xx.x) / N	xx (xx.x) / N
Week 12	xx (xx.x) / N	xx (xx.x) / N	xx (xx.x) / N	xx (xx.x) / N	xx (xx.x) / N
Week 13	xx (xx.x) / N	xx (xx.x) / N	xx (xx.x) / N	xx (xx.x) / N	xx (xx.x) / N
Week 14	xx (xx.x) / N	xx (xx.x) / N	xx (xx.x) / N	xx (xx.x) / N	xx (xx.x) / N
Week 15	xx (xx.x) / N	xx (xx.x) / N	xx (xx.x) / N	xx (xx.x) / N	xx (xx.x) / N
Week 16	xx (xx.x) / N	xx (xx.x) / N	xx (xx.x) / N	xx (xx.x) / N	xx (xx.x) / N
Week 18	xx (xx.x) / N	xx (xx.x) / N	xx (xx.x) / N	xx (xx.x) / N	xx (xx.x) / N
Week 26	xx (xx.x) / N	xx (xx.x) / N	xx (xx.x) / N	xx (xx.x) / N	xx (xx.x) / N
Week 38	xx (xx.x) / N	xx (xx.x) / N	xx (xx.x) / N	xx (xx.x) / N	xx (xx.x) / N
Week 52	xx (xx.x) / N	xx (xx.x) / N	xx (xx.x) / N	xx (xx.x) / N	xx (xx.x) / N

^{*} Number of Participants be analyzed.

Table 3.1.4 Summary of QTcF Changes from Baseline Value by Treatment Arm

Visit Arm D0 Mean /N*	1 Arm 2	Arm 3	Arm 4	Arm 5
	D400	D800-OD	D1200	D800-BD
	Mean (SE) /N	Mean (SE) /N	Mean (SE) /N	Mean (SE) /N

Baseline	0	0	0	0	0
Week 01	xx (xx.x) / N				
Week 02	xx (xx.x)/N	xx (xx.x) / N			
Week 03	xx (xx.x)/N	xx (xx.x) / N			
Week 04	xx (xx.x) / N				
Week 05	xx (xx.x) / N				
Week 06	xx (xx.x) / N				
Week 07	xx (xx.x) / N				
Week 08	xx (xx.x) / N				
Week 09	xx (xx.x) / N				
Week 10	xx (xx.x) / N	xx (xx.x)/N	xx (xx.x) / N	xx (xx.x) / N	xx (xx.x) / N
Week 11	xx (xx.x) / N				
Week 12	xx (xx.x) / N				
Week 13	xx (xx.x) / N				
Week 14	xx (xx.x) / N				
Week 15	xx (xx.x) / N				
Week 16	xx (xx.x) / N				
Week 18	xx (xx.x) / N				
Week 26	xx (xx.x) / N				
Week 38	xx (xx.x) / N				
Week 52	xx (xx.x) / N				

QT Table 3.1.5 Summary of QT Actual Value by Visit

{Similar shell table as Table 3.1.1}

Table 3.1.6 Participants Proportion of QT Changes from Baseline by Treatment Arm $\{ Similar\ shell\ table\ as\ Table\ 3.1.2 \}$

Table 3.1.7 Summary of QT Actual Value by Visit

{Similar shell table as Table 3.1.3}

Table 3.1.8 Summary of QT Changes from Baseline Value by Treatment Arm

{Similar shell table as Table 3.1.4}

PR:

Table 3.1.9 Summary of PR Actual Value by Visit

{Similar shell table as Table 3.1.1}

Page 36 of 46

Table 3.1.10 Participants Proportion of PR Changes from Baseline by Treatment Arm

{Similar shell table as Table 3.1.2}

Table 3.1.11 Summary of PR Actual Value by Visit

(Similar shell table as Table 3.1.3)

Table 3.1.12 Summary of PR Changes from Baseline Value by Treatment Arm

{Similar shell table as Table 3.1.4}

RR

Table 3.1.13 Summary of RR Actual Value by Visit

{Similar shell table as Table 3.1.1}

Table 3.1.14 Participants Proportion of RR Changes from Baseline by Treatment Arm {Similar shell table as Table 3.1.2}

Table 3.1.15 Summary of RR Actual Value by Visit

{Similar shell table as Table 3.1.3

Table 3.1.16 Summary of RR Changes from Baseline Value by Treatment Arm

{Similar shell table as Table 3.1.4}

ORS

Table 3.1.17 Summary of QRS Actual Value by Visit

{Similar shell table as Table 3.1.1}

Table 3.1.18 Participants Proportion of QRS Changes from Baseline by Treatment Arm

{Similar shell table as Table 3.1.2}

Table 3.1.19 Summary of QRS Actual Value by Visit

{Similar shell table as Table 3.1.3}

Table 3.1.20 Summary of QRS Changes from Baseline Value by Treatment Arm

{Similar shell table as Table 3.1.4}

Page 37 of 46

Heart Rate (HR)

Table 3.1.21 Summary of HR Actual Value by Visit

{Similar shell table as Table 3.1.1}

Table 3.1.22 Participants Proportion of HR Changes from Baseline by Treatment Arm

{Similar shell table as Table 3.1.2}

Table 3.1.23 Summary of HR Actual Value by Visit

{Similar shell table as Table 3.1.3}

Table 3.1.24 Summary of HR Changes from Baseline Value by Treatment Arm

{Similar shell table as Table 3.1.4}

3.2 Safety Laboratory

Serum Chemistry

These tables will be produced for ALT, AST, Total Bilirubin, Gamma-Glutamyl Transferase, Potassium, Alkaline Phosphatase (ALP), Creatinine.

ALT

Table 3.2.1 Summary of Group Mean ALT (x ULN) Changes over time

Visit	Arm 1	Arm 2	Arm 3	Arm 4	Arm 5
	D0	D400	D800-OD	D1200	D800-BD
	Mean (SE)	Mean (SE) /N	Mean (SE) /N	Mean (SE) /N	Mean (SE) /N
	/N	5 2	ny 25	8 92	, ,
Baseline	xx (xx.x) / N				
Week 01	xx (xx.x) / N				
Week 02	xx (xx.x) / N				
Week 03	xx (xx.x) / N				
Week 04	xx (xx.x) / N				
Week 05	xx (xx.x) / N				
Week 06	xx (xx.x) / N				
Week 07	xx (xx.x) / N				
Week 08	xx (xx.x) / N				
Week 09	xx (xx.x) / N				
Week 10	xx (xx.x) / N				
Week 11	xx (xx.x) / N				
Week 12	xx (xx.x) / N				
Week 13	xx (xx.x) / N				
Week 14	xx (xx.x) / N				
Week 15	xx (xx.x) / N				
Week 16	xx (xx.x) / N				
Week 18	xx (xx.x) / N				
Week 26	xx (xx.x) / N				

Page **38** of **46**

PanACEA - DECODE - 01

v1.0, February 13, 2023

| Week 38 | xx (xx.x) / N |
|---------|---------------|---------------|---------------|---------------|---------------|
| Week 52 | xx (xx.x) / N |

Table 3.2.2 Summary of Absolute value ALT (IU/L) Changes over time

Visit	Arm 1 D0 Mean (SE) /N	Arm 2 D400 Mean (SE) /N	Arm 3 D800-OD Mean (SE) /N	Arm 4 D1200 Mean (SE) /N	Arm 5 D800-BD Mean (SE) /N
Baseline	0	0	0	0	0
Week 01	xx (xx.x) / N	xx (xx.x) / N	xx (xx.x) / N	xx (xx.x) / N	xx (xx.x) / N
Week 02	xx (xx.x) / N	xx (xx.x) / N	xx (xx.x) / N	xx (xx.x) / N	xx (xx.x) / N
Week 03	xx (xx.x) / N	xx (xx.x) / N	xx (xx.x)/N	xx (xx.x) / N	xx (xx.x) / N
Week 04	xx (xx.x) / N	xx (xx.x)/N	xx (xx.x)/N	xx (xx.x) / N	xx (xx.x) / N
Week 05	xx (xx.x) / N	xx (xx.x) / N	xx (xx.x) / N	xx (xx.x) / N	xx (xx.x) / N
Week 06	xx (xx.x) / N	xx (xx.x)/N	xx (xx.x)/N	xx (xx.x) / N	xx (xx.x) / N
Week 07	xx (xx.x) / N	xx (xx.x) / N	xx (xx.x) / N	xx (xx.x) / N	xx (xx.x) / N
Week 08	xx (xx.x) / N	xx (xx.x) / N	xx (xx.x) / N	xx (xx.x) / N	xx (xx.x) / N
Week 09	xx (xx.x) / N	xx (xx.x) / N	xx (xx.x) / N	xx (xx.x) / N	xx (xx.x) / N
Week 10	xx (xx.x) / N	xx (xx.x) / N	xx (xx.x) / N	xx (xx.x) / N	xx (xx.x) / N
Week 11	xx (xx.x) / N	xx (xx.x) / N	xx (xx.x) / N	xx (xx.x) / N	xx (xx.x) / N
Week 12	xx (xx.x) / N	xx (xx.x) / N	xx (xx.x) / N	xx (xx.x) / N	xx (xx.x) / N
Week 13	xx (xx.x) / N	xx (xx.x) / N	xx (xx.x) / N	xx (xx.x) / N	xx (xx.x) / N
Week 14	xx (xx.x) / N	xx (xx.x) / N	xx (xx.x) / N	xx (xx.x) / N	xx (xx.x) / N
Week 15	xx (xx.x) / N	xx (xx.x) / N	xx (xx.x) / N	xx (xx.x) / N	xx (xx.x) / N
Week 16	xx (xx.x) / N	xx (xx.x)/N	xx (xx.x) / N	xx (xx.x) / N	xx (xx.x) / N
Week 18	xx (xx.x) / N	xx (xx.x)/N	xx (xx.x) / N	xx (xx.x) / N	xx (xx.x) / N
Week 26	xx (xx.x) / N	xx (xx.x)/N	xx (xx.x) / N	xx (xx.x) / N	xx (xx.x) / N
Week 38	xx (xx.x) / N	xx (xx.x)/N	xx (xx.x) / N	xx (xx.x) / N	xx (xx.x) / N
Week 52	xx (xx.x) / N	xx (xx.x) / N	xx (xx.x) / N	xx (xx.x) / N	xx (xx.x) / N

AST

Table 3.2.3 Summary of Group Mean AST (x ULN) Changes over time

{Similar shell table as Table 3.2.1}

Table 3.2.4 Summary of Absolute value AST (IU/L) Changes over time

{Similar shell table as Table 3.2.2}

Total Bilirubin

Table 3.2.5 Summary of Group Mean Total Bilirubin (x ULN) Changes over time

{Similar shell table as Table 3.2.1}

Page **39** of **46**

Table 3.2.6 Summary of Absolute value Total Bilirubin (UMOL/L) Changes over time {Similar shell table as Table 3.2.2}

Gamma-Glutamyl Transferase

Table 3.2.7 Summary of Group Mean Gamma-Glutamyl Transferase (x ULN) Changes over time {Similar shell table as Table 3.2.1}

Table 3.2.8 Summary of Absolute value Gamma-Glutamyl Transferase (UMOL/L) Changes over time {Similar shell table as Table 3.2.2}

Alkaline Phosphatase (ALP)

Table 3.2.9 Summary of Group Mean Alkaline Phosphatase (ALP) (x ULN) Changes over time {Similar shell table as Table 3.2.1}

Table 3.2.10 Summary of Absolute value Alkaline Phosphatase (ALP) (IU/L) Changes over time {Similar shell table as Table 3.2.2}

Potassium

Table 3.2.11 Summary of Group Mean Potassium (x ULN) Changes over time*

{Similar shell table as Table 3.2.1}

Table 3.2.12 Summary of Absolute value Potassium (mmol/L) Changes over time*

{Similar shell table as Table 3.2.2}

*Tables will be repeated as a sensitivity analysis excluding outliers.

Sodium

Table 3.2.13 Summary of Group Mean Sodium (x ULN) Changes over time*

{Similar shell table as Table 3.2.1}

Table 3.2.14 Summary of Absolute value Sodium (mmol/L) Changes over time*

{Similar shell table as Table 3.2.2}

*Tables will be repeated as a sensitivity analysis excluding outliers.

Creatinine

Table 3.2.15 Summary of Group Mean Potassium (x ULN) Changes over time

{Similar shell table as Table 3.2.1}

Table 3.2.16 Summary of Absolute value Potassium (umol/L) Changes over time

{Similar shell table as Table 3.2.2}

Haematology and Coagulation Results

Platelet Count

Table 3.2.17 Summary of Group Mean Platelet Count Changes over time

{Similar shell table as Table 3.2.1}

Haemoglobin

Table 3.2.18 Summary of Group Mean Platelet Count Changes over time

{Similar shell table as Table 3.2.1}

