## 14.2 Clarifications and exceptions

Occurrences will be registered as AE from administration of the first dose of study drugs. All events that occur or are elicited before administering any study drugs, e.g. screening laboratory abnormalities qualifying as Adverse Events, will be recorded as medical history. If such events meet criteria for seriousness, they will nevertheless be reported as SAEs.

Abnormalities which are not clinically significant as per the qualified judgement of the investigator do not constitute adverse events and are not recorded and reported as such. However, these abnormalities may be analysed and reported in the study report.

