#### Action Taken with Study Drugs

- IMP unchanged
- IMP interrupted
- IMP stopped
- Non IMP study drug unchanged
- Non IMP study drugs interrupted
- Non IMP study drugs stopped
- Not applicable

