5.2.1. Secondary Safety Endpoints

- All adverse events
- · Adverse events of Grade 3 severity or higher
- · Adverse events possibly, probably or definitely related to study drugs
- · Treatment discontinuations or interruptions related to adverse events/serious adverse events
- · Frequency, severity and type of ECG alterations
- Changes in ECG intervals of PR, RR, QRS, QT, Fridericia-corrected QT [QTcF]
- Proportion of participants with QTcF > 500ms in ECGs on treatment
- Proportion of participants with a prolongation of QTcF > 60ms in ECGs of grade 3 and above as defined in the protocol

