Appendix: Shells of tables and listings

This section presents the shells for the planned Tables and Listings to be programmed in support of the planned analyses identified in the SAP. This section is intended to support the SAP and provides guidance on the programming specifications (shells) for the planned outputs and may be updated, with any updates appropriately documented, reviewed, and approved.

1. Demographic and Baseline

Table 1.1 Participant Disposition - All Participants Screened

	Arm 1 D0 (N=x) n (%)	Arm 2 D400 (N=x) n (%)	Arm 3 D800-OD (N=x) n (%)	Arm 4 D1200 (N=x) n (%)	Arm 5 D800-BD (N=x) n (%)	Total (N=x) n (%)
Screened for Eligibility						x
Randomized	xx (xx.x %)	xx (xx.x %)	xx (xx.x %)	xx (xx.x %)	xx (xx.x %)	xx (xx.x %)
Screen Failure [1]						x
Reason 1						x
Reason 2						x
Reason 3						x
Others						x

^[1] Participants who have not met eligibility criteria, or otherwise chose not to participate in the study.

Table 1.2 Participant Disposition - All Participants Randomized

	Arm 1 D0 (N=x) n (%)	Arm 2 D400 (N=x) n (%)	Arm 3 D800-OD (N=x) n (%)	Arm 4 D1200 (N=x) n (%)	Arm 5 D800-BD (N=x) n (%)	Total (N=x) n (%)
Randomized	xx (xx.x %)	xx (xx.x %)	xx (xx.x %)	xx (xx.x %)	xx (xx.x %)	xx (xx.x %)
Intent-To- Treat Population [2]	xx (xx.x %)	xx (xx.x %)	xx (xx.x %)	xx (xx.x %)	xx (xx.x %)	xx (xx.x %)
Adequate adherence (AA) population	xx (xx.x %)	xx (xx.x %)	xx (xx.x %)	xx (xx.x %)	xx (xx.x %)	xx (xx.x %)
Safety Population	xx (xx.x %)	xx (xx.x %)	xx (xx.x %)	xx (xx.x %)	xx (xx.x %)	xx (xx.x %)
Completed Study	xx (xx.x %)	xx (xx.x %)	xx (xx.x %)	xx (xx.x %)	xx (xx.x %)	xx (xx.x %)
Discontinued Early	xx (xx.x %)	xx (xx.x %)	xx (xx.x %)	xx (xx.x %)	xx (xx.x %)	xx (xx.x %)
Adverse Event	xx (xx.x %)	xx (xx.x %)	xx (xx.x %)	xx (xx.x %)	xx (xx.x %)	xx (xx.x %)
Subject Withdrawal of Consent	xx (xx.x %)	xx (xx.x %)	xx (xx.x %)	xx (xx.x %)	xx (xx.x %)	xx (xx.x %)

^[2] The ITT population will consist of all randomized participants in the groups to which they were randomly assigned, and who have taken at least one dose of study treatment.

v1.0, February 13, 2023

Table 1.3 Major Protocol Deviations Intent-To-Treat Population

Major Protocol Deviation Category	Arm 1 D0 (N=x) n (%)	Arm 2 D400 (N=x) n (%)	Arm 3 D800-OD (N=x) n (%)	Arm 4 D1200 (N=x) n (%)	Arm 5 D800-BD (N=x) n (%)	Total (N=x) n (%)
Participants with any Major Deviation	xx (xx.x %)	xx (xx.x %)	xx (xx.x %)	xx (xx.x %)	xx (xx.x %)	xx (xx.x %)

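### Minor reporting improvement: all 18 laboratory shells in SAP Appendix 3.2 are arm means by visit; add descriptive patient counts at the protocol's liver criteria, a joint ALT/AST-bilirubin count and a low-potassium count

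*SAP*

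**What the plan says.** SAP Appendix 3.2 has 18 laboratory shells. Tables 3.2.1 to 3.2.16 take eight chemistry analytes twice each, once as a multiple of ULN and once in absolute units. Tables 3.2.17 and 3.2.18 sit under the platelet and haemoglobin headings. The model layout is "Table 3.2.1 Summary of Group Mean ALT (x ULN) Changes over time", with mean (SE) and N by arm and visit, and the rest refer back to it or to its absolute-value twin. Potassium follows the same pattern, starting with "Table 3.2.11 Summary of Group Mean Potassium (x ULN) Changes over time" and continuing with a table in mmol/L. For potassium and sodium a footnote adds: "Tables will be repeated as a sensitivity analysis excluding outliers". One heading reads "Haematology and Coagulation Results", but no shell shows INR.

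The protocol works patient by patient. Section 20.1.2 starts close observation above 3x ULN. Section 13.10 lists four reasons to discontinue study drug: ALT or AST above 8x ULN; above 5x ULN lasting more than 2 weeks; above 3x ULN with bilirubin above 2x ULN or INR above 1.5; and above 3x ULN with symptoms, rash or eosinophilia. Section 20.1.3 repeats the list but asks only that a pause be considered.

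Several other outputs operate at patient level:
- SAP 7.3 tabulates patients who discontinue under protocol 13.10.
- SAP 5.2.1 has the secondary endpoint "Treatment discontinuations or interruptions related to adverse events/serious adverse events", and protocol 14.7 codes "IMP interrupted" for each event.
- SAP 13.2 undertakes to tabulate patients who worsen from baseline, laboratory parameters included, without saying what counts as worse.
- Protocol 14.2 limits the adverse event route: "Abnormalities which are not clinically significant as per the qualified judgement of the investigator do not constitute adverse events". It then says that such abnormalities may still be analysed and reported.

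**The concern.** Liver injury and hypokalaemia happen to individuals. A mean of about 15 values does not give the number of patients past a cut-off, and two separate tables of means cannot identify a patient in whom ALT/AST and bilirubin are both raised. Protocol 20.1 gives adequate characterisation of the regimen's liver risk as a reason for its approach, and arm means do not deliver that.

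Potassium matters here because three study drugs can prolong QT (protocol 7.4) and hypokalaemia is named as a risk factor for delamanid-associated QTc prolongation (protocol 7.2.2). The relevant direction is downwards, yet one of the two potassium tables is scaled to the upper limit. SAP 13.1.1 already gives patient categories and highest values for QTcF. The laboratory data have no counterpart.

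**Working it through.** The plan states no figure on this point, so there is none to reproduce. The check is an audit of the shells followed by illustrations. The ALT and potassium baselines are assumptions, because the documents give none. The arm size of 15, with up to 3 drop-outs, is from SAP 4.3.

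**1. Shell audit.** Of Tables 3.2.1 to 3.2.18, 18 are arm means by visit. None counts patients at a threshold, none joins ALT/AST to bilirubin or INR, and none counts low potassium.

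**2. One patient with raised ALT.** Arm mean = (14b + x)/15, where b is the level of the other 14 patients and x is the raised value, both in multiples of ULN.

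| b (assumed) | x = 3 | x = 5 |
|---|---|---|
| 0.4 | 0.57 | 0.71 |
| 0.6 | 0.76 | 0.89 |
| 0.8 | 0.95 | 1.08 |

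**3. Same mean, different patients.** Four patients at 1.7x and 11 at 0.6x, none past any protocol cut-off, give (11 x 0.6 + 4 x 1.7)/15 = 13.4/15 = 0.89x. This equals the mean with one patient at 5x. The SEs differ:
- One at 5x: (5 - 0.6)/15 = 0.29.
- Four at 1.7x: sqrt[(11 x 4/15) x 1.1^2 / 14 / 15] = 0.13.

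The larger SE hints at spread but does not say how many patients are affected.

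**4. Joint criterion.** Take the patient with raised ALT and swap that patient's bilirubin value with another patient's in the same arm. Both means and both SEs are unchanged. Separate tables therefore cannot show a joint rise, whatever the arm size.

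**5. Potassium.** Change in arm mean = (low value - 4.2)/n, with 4.2 mmol/L assumed typical.
- n = 15: a value of 2.8 gives -0.09; 3.2 gives -0.07; 2.4 gives -0.12 mmol/L.
- n = 12 (after 3 drop-outs): a value of 2.8 gives -0.12 mmol/L.

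**6. Unscheduled retests.** Above 3x ULN, protocol 20.1.2 repeats liver tests two or three times weekly and wants the results in the database. For by-visit tables, SAP 12.6 keeps only the visit nearest the target. For week 5 (days 32 to 38, target 35), a retest further from day 35 than the scheduled visit drops out. A peak may therefore be in the database but not in the table. The documents give no basis for saying how often.

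**7. Precision of the proposed counts.** Exact 95% intervals are 0.2% to 31.9% for 1/15 and 0% to 21.8% for 0/15. At an assumed true rate of 2%, the chance of at least one case in an arm of 15 is 1 - 0.98^15 = 26%; at 5% it is 54% and at 10% it is 79%.

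**The case against.** The strongest reply is that most of the serious cases are already caught. Each of the four liver criteria is a reason to discontinue, and SAP 7.3 tabulates patients who discontinue under them. Toxicity leading to a planned deviation from study medication is immediately reportable (protocol 14.3). Adverse events are summarised by preferred term and maximum severity, and event-related interruptions are a secondary endpoint. SAP 13.2 promises a patient-level tabulation of worsening. The shells are described as something that "provides guidance on the programming specifications (shells) for the planned outputs and may be updated", so a missing shell is not a missing analysis.

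Much of this stands, and it narrows the gap without closing it. SAP 7.3 reaches only patients who discontinue. A patient without symptoms who is above 3x ULN with normal bilirubin and INR is only observed more closely, and protocol 20.1.3 leaves a pause to be considered. Adverse event status rests on the investigator's judgement. Protocol 14.2 permits reporting of the remaining abnormalities but does not commit to it. SAP 13.2 sets no threshold.

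Two further replies carry weight. Coagulation is scheduled only at screening and week 2, so the missing INR shell matters little and any INR count depends on who was tested. The protocol has no on-treatment potassium cut-off, and SAP 13.1.1 displays QTcF prolongation, the feared consequence, directly.

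A reader might infer that the plan leaves liver injury or hypokalaemia unreported at patient level, or that low potassium values are removed from the analysis. The documents support neither. The outputs above cover part of the ground, a table in mmol/L is planned, and the exclusion of outliers applies only to a sensitivity repeat. The fault there is that outlier has no definition for safety data.

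**Conclusion.** The point holds as a minor improvement to descriptive safety reporting. All 18 laboratory shells are arm means, and these cannot answer the patient-level questions that the protocol's own liver rules raise. Three things remain without a specified display: patients who cross a cut-off without discontinuing and without an adverse event record, the joint ALT/AST-bilirubin picture, and low potassium.

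The size is illustrative. Under the assumed baselines, one patient at 5x ULN leaves the arm mean between 0.71x and 1.08x, and one potassium value of 2.8 mmol/L moves the arm mean by about 0.09 mmol/L. The audit of the shells and the argument about the joint criterion need no assumption.

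It would be wrong to conclude that the primary endpoints or the choice of dose are at risk. Neither uses these tables, and counts in arms of 15 could not support a comparison between doses.

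**What to change.** In SAP 13.2, define laboratory worsening. In Appendix 3.2, make the following changes, with the counts shown by arm and based on all on-treatment values including unscheduled ones:

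1. n (%) with maximum ALT or AST above 3x and above 8x ULN, and n (%) above 5x ULN for more than 2 weeks. A single maximum above 5x may be an extra category, labelled as not a protocol criterion.
2. n (%) with ALT/AST above 3x ULN together with bilirubin above 2x ULN, or INR above 1.5 where tested; and n (%) meeting the criterion of above 3x ULN with symptoms, rash or eosinophilia.
3. n (%) with lowest potassium below the laboratory lower limit, by CTCAE 5.0 grade. This replaces the potassium table in multiples of ULN; the mmol/L table stays.
4. Limit the repeat that excludes outliers to confirmed sample errors.

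Label the counts descriptive. The other mean tables stay.

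The cost is a few lines of SAP text and two or three extra tables, with no new procedure or data. The drawback is imprecise counts. The appendix allows updates and needs an edit in any case: the creatinine tables are titled as potassium and the haemoglobin table as platelet count.
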